### b. Secondary Objectives:

- i. To determine whether HD-TIV compared with SD-QIV will increase the probability of achieving a  $\geq 4$ -fold rise in HAI titers,  $\geq 1:40$  HAI titer, or higher GMT titers to influenza B antigens in adult HSCT recipients.
- ii. To determine the frequency and severity of solicited local injection site adverse events (e.g. pain/ tenderness, redness, and swelling/induration at injection site) with HD-TIV compared to SD-QIV in adult HSCT recipients.
- iii. To determine the frequency and severity of solicited systemic adverse events (e.g. fevers, headache, fatigue/malaise, nausea, body ache/myalgia, general activity level, and vomiting) with HD-TIV compared to SD-QIV in adult HSCT recipients.
- iv. To define the relationship between HAI titers, *in vivo* T and B cell phenotype, and *in vitro* influenza-specific T and B cell response in adult HSCT recipients receiving either HD-TIV or SD-QIV.
- v. To correlate HAI responses to MN responses.
- vi. To compare the persistent HAI and MN titers for all four antigen seven months after the last vaccine dose to assess for persistence of antibody titers.
- vii. To compare influenza detection by PCR during influenza season in adult HSCT recipients receiving either HD-TIV or SD-QIV.
- viii. To assess HAI and MN response in patients (e.g. repeaters) undergoing two-consecutive years revaccination using the same antigen dose
- ix. To correlate HAI responses to neuraminidase inhibition titers (NAI).

**3. Study Area:** The study will be conducted in the Oncology Units or Clinics, or Clinical Trial Centers at the following sites: **Table 2** includes the yearly average number of transplants per site.

Table 2. Clinical Sites	Average Number of Yearly Allogeneic Transplants
Northwestern University Feinberg School of Medicine	167
Fred Hutchinson Cancer Research Center	300
University Hospital, University of Alabama at Birmingham	90
Vanderbilt University Medical Center	108
TOTAL	665

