**5. Inclusion of Quadrivalent Inactivated Influenza Vaccine (QIV).** Although two influenza B lineages have been co-circulating since the 1980s, TIV contains only one B strain, which provides little to no protection against the alternate B-lineage strain; however, about 70% of recent B virus infections have been antigenically related to the B virus component of the trivalent flu vaccines. A SD-QIV is currently available and provides additional protection against the second B strain while retaining non-inferior immunogenicity to the other 3 TIV strains.

**6. Rationale.** Patients who have undergone HSCTs have a higher burden of disease from influenza infection compared with healthy controls, with significant morbidity and mortality due to influenza disease. They are also

at high risk of influenza-associated complications, particularly pneumonia. Thus, strategies to reduce influenza disease in this highly susceptible population are critical, especially since these individuals respond poorly to SD IIV. HD-TIV has increased immunogenicity and efficacy in adults  $\geq 65$  years compared with SD, and in many phase I studies in an immunocompromised population, there are data suggesting that HD may have increased immunogenicity. Therefore, the use of HD-TIV appears to be a promising and practical alternative intervention to improve vaccine-induced immune responses in adult HSCT recipients. ***We hypothesize that HD-TIV will be more immunogenic compared with SD-QIV and will remain well tolerated in this vulnerable population.*** Thus, for this protocol we propose to conduct a phase II trial and compare the immunogenicity and safety of HD-TIV to SD-QIV in adult stem cell transplant recipients.

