## 10. Investigational Product and Risk Information:

Fluzone Quadrivalent® is a Federal Drug Administration (FDA)-approved vaccine and is recommended for all patients ≥6 months.

Fluzone® HD-TIV has not yet been approved for individuals <65 years of age. The current seasonal influenza vaccine will be used throughout the entire study.

- a. **Acquisition:** Fluzone Quadrivalent® and Fluzone® HD, preservative free, licensed product formulated for the 2017-2018, 2018/2019, and/or 2019/2020 influenza season will be donated by Sanofi Pasteur and distributed to each site of the 4 institutions.
- b. **Formulation, Packaging, and Labeling:** Fluzone Quadrivalent® and Fluzone® HD, preservative free, licensed product, Sanofi Pasteur, Swiftwater, PA. The 2017-2018 influenza strain recommendations are the following: A/Michigan/45/2015 (H1N1)-like virus; an A/Hong Kong/4801/2014 (H3N2)-like virus; and a B/Brisbane/60/2008-like virus (this is a B/Victoria lineage virus) for both HD-TIV and SD-QIV; and in Fluzone Quadrivalent®, additional B virus, B/Phuket/3073/2013-like virus (this is a B/Yamagata lineage virus). The Fluzone package inserts for the 2017-2018 influenza season for both vaccines will be available in the Protocol Library.
- c. Fluzone Quadrivalent® and Fluzone® HD, preservative free, licensed product formulated for the 2018-2019 influenza season, Sanofi Pasteur, Swiftwater, PA will be obtained. Formulation, Packaging, and Labeling: Fluzone Quadrivalent® and Fluzone® HD, preservative free, licensed product, Sanofi Pasteur, Swiftwater, PA. The 2018-2019 recommendations are the following: A/Michigan/45/2015 (H1N1)pdm09-like virus; an A/Singapore/INFIMH-16-0019/2016 (H3N2)-like virus; and a B/Colorado/06/2017-like virus (this is a B/ Victoria lineage virus); and in Fluzone Quadrivalent®, additional B virus, B/Phuket/3073/2013-like virus, (this is a B/ Yamagata lineage virus). The Fluzone package inserts for the 2018-2019 influenza season for both vaccines will be available in the Protocol Library.

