- d. The 2019-2020 influenza strain recommendations are the following: A/Brisbane/02/2018 (H1N1)pdm09-like virus; A/Kansas/14/2017 (H3N2)-like virus; and B/Colorado/06/2017-like virus (B/Victoria/2/87 lineage) for both HD-TIV and SD-QIV; and in Fluzone Quadrivalent®, additional B virus, B/Phuket/3073/2013-like virus (B/Yamagata lineage). The Fluzone package inserts for the 2019-2020 influenza season for both vaccines will be available in the Protocol Library.

**c. Product Storage and Stability:** The vaccine will be stored in the original package to protect from light. The vaccine will be stored in secure, limited-access, temperature-monitored refrigerator environments at 2°C to 8°C (35.6°F to 46.4°F) until needed. The temperature of the storage unit will be monitored for the duration of the trial, and documentation of proper dedicated storage will be maintained. It will not be frozen. In the event of accidental deep-freezing or disruption of the cold chain, vaccines will not be administered.

**d. Dosage, Preparation and Administration of Study Intervention/ Investigational Product:** Either dose (0.5 ml) of SD-QIV or HD-TIV (Fluzone Quadrivalent®, Sanofi Pasteur or Fluzone® HD-TIV, Sanofi Pasteur) will be administered intramuscularly in either the right or left arm. In preparing either vaccine, the pre-filled syringe will be gently shaken and visually inspected for particulate matter and/or discoloration prior to administration (the SD-QIV/HD-TIV may normally be clear to slightly opalescent). If either condition exists, the pre-filled syringe will not be used.

Subjects are randomized in a 1:1 fashion to receive either 2 doses of 0.5ml of HD-TIV (60µg of each influenza antigen) or 2 doses of SD-QIV (15 µg of each influenza antigen) of the current seasonal influenza vaccine (e.g. 2017-2018 or 2018/2019), 28-42 days apart. The repeaters retain their randomization code.

Each of these study products will be labeled according to manufacturer specifications and include the statement “Caution: New Drug-Limited by Federal Law to Investigational Use”.

**e. Modification of Study Intervention/Investigational Product for a Participant:** No dose modifications will be allowed.

**11. Side Effects with Influenza Vaccination.** The side effects listed in the package insert include:

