## 15. Laboratory Procedures:

- a. **Specimen Preparation, Handling, and Shipping:** Blood will be collected from a vein or from a central line from subjects. . Study personnel or clinical research staff or clinic nurse will collect the blood samples, label without personal identifiers, and deliver to the laboratory for preparation of serum and freezing of the sera until further testing and/or shipment to Vanderbilt University Medical Center for HAI, MN testing, B and T cell influenza-specific responses. Other clinical labs will be sent the local lab.
- b. **Hemagglutination Inhibition Assays (HAI):** Sera HAI testing will be tested at Vanderbilt University Medical Center. Sera will be initially diluted 1:10 per protocol. Pre-vaccination and post-vaccination sera will be analyzed simultaneously to minimize variability in the HAI assay. HAI titers will be determined for each influenza antigen included in QIV 2017-2018 or 2018-2019.
- c. **Microneutralization assays:** Sera will be shipped to at Vanderbilt University Medical Center for MN testing and results will be compared to HAI.
- d. **Neuraminidase inhibition titers.** Sera will be shipped to at Vanderbilt University Medical Center for NAi testing and results will be compared to HAI.
- e. **Influenza-specific B and T cell Responses and Immunophenotyping of B and T cells:** Samples will be collected at baseline, 5-10 days (optional) and 28-42 days after each vaccination and 5-9 months after second vaccination. After ficoll separation, peripheral blood mononuclear cells (PBMC) will be cryopreserved for future analysis. Each site will do this locally and the off-sites will ship to **[name]** laboratory at Vanderbilt in Nashville, TN. This will ensure all time points from each individual can be evaluated simultaneously. We propose to study B and T cell responses to vaccination with mass cytometry technology (CyTOF), and functional assays such as *in-vitro* IL-21 production in response to vaccine antigen.
- f. **Nasal swabs:** a nasal swab will be collected and shipped to Vanderbilt University Medical Center in Nashville, TN for PCR testing for influenza.

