groups will be estimated by calculating the posterior 95% credible interval of the difference in proportions. For continuous-valued events (e.g. size of swelling) uninformative priors will be used as described in (17.b); for discrete events, a flat beta parameter with scale=shape=1 will be used as uninformative priors. For each group and each event, solicited and unsolicited AEs will be descriptively summarized. Severities of solicited and unsolicited AEs will also be descriptively summarized for each group and each type of event. Descriptive statistics will include number experiencing event, mean and 95% posterior credible interval. Maximum size of redness and swelling may be descriptively summarized for each group and event; proportion of events lasting longer beyond Day 3 may also be descriptively summarized. Subjects with missing data will be excluded from analysis, but the sensitivity of the results to missingness will be formally analyzed by comparing posterior estimates under the range of possible outcomes for the missing individuals.

- d. Influenza-Like-Illness assessment:** The percentage of individuals in each group that test positive for influenza by PCR and the number of ILIs in each group during the influenza season will be compared.

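### The antigen set needs two corrections: HAI testing does not name the 2019-2020 strains given to repeaters, and the influenza B objective does not set aside a lineage that HD-TIV lacks

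*Combined protocol and SAP*

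**What the plan says.** **HAI panel.** Section C.15.b states: "HAI titers will be determined for each influenza antigen included in QIV 2017-2018 or 2018-2019". It makes no distinction by arm and mentions no later season.

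**2019-2020 vaccination.** Sections C.1 and C.4 allow subjects first enrolled in 2018-2019 to return in 2019-2020 and receive the same assigned vaccine type. Section C.10 supplies vaccine for that season and lists its influenza A strains as "A/Brisbane/02/2018 (H1N1)pdm09-like virus; A/Kansas/14/2017 (H3N2)-like virus". Secondary objective (viii) asks for the HAI and MN response of repeaters over two consecutive years.

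**Influenza B objective.** Secondary objective (i) is directional. It asks whether HD-TIV, compared with SD-QIV, makes a four-fold rise or a titer of at least 1:40 more likely, "or higher GMT titers to influenza B antigens in adult HSCT recipients". No lineage is named. Objective (vi) compares persistence for all four antigens.

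**Vaccine content.** For 2017-2018, section C.10 adds to the strains common to both vaccines "and in Fluzone Quadrivalent®, additional B virus, B/Phuket/3073/2013-like virus (this is a B/Yamagata lineage virus"). The 2018-2019 and 2019-2020 paragraphs give the quadrivalent product the same extra strain. Section B.5 says that "TIV contains only one B strain, which provides little to no protection against the alternate B-lineage strain".

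**The concern.** Two parts of the plan do not fit the vaccines that the subjects receive.

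First, a laboratory that follows section C.15.b as written would test the sera of 2019-2020 repeaters against earlier seasons' influenza A strains. Influenza A is the main interest of the trial. Titers against superseded strains would not measure the response to either influenza A component of the vaccine given that season.

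Second, B/Yamagata titers will be produced in both arms, and nothing in objective (i), section C.15.b or section C.17.b says how they enter the influenza B comparison. If they enter on the same footing as B/Victoria, a question about dose is mixed with a difference in vaccine content. The choice of which B antigens count would then be made after the data exist.

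**Working it through.** **1. Strains by season (section C.10)**

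| Component | 2017-18 | 2018-19 | 2019-20 | In HD-TIV? |
|---|---|---|---|---|
| H1N1 | A/Michigan/45/2015 | A/Michigan/45/2015 | A/Brisbane/02/2018 | yes |
| H3N2 | A/Hong Kong/4801/2014 | A/Singapore/INFIMH-16-0019/2016 | A/Kansas/14/2017 | yes |
| B/Victoria | B/Brisbane/60/2008 | B/Colorado/06/2017 | B/Colorado/06/2017 | yes |
| B/Yamagata | B/Phuket/3073/2013 | B/Phuket/3073/2013 | B/Phuket/3073/2013 | no, in 3 of 3 seasons |

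**2. Coverage of the HAI panel.** The two seasons named in section C.15.b contain 4 + 2 = 6 distinct strains, because 2018-19 adds A/Singapore and B/Colorado. Adding 2019-20 makes 6 + 2 = 8, the new ones being A/Brisbane and A/Kansas. So 2 of the 4 strains in the 2019-20 quadrivalent vaccine are outside the named panel, and they are both of its influenza A strains. The other two, both B, are inside it because they did not change.

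**3. What the B contrast measures.** Section C.1 gives 60 µg per antigen for HD-TIV and 15 µg for SD-QIV.
- B/Victoria: 60 µg against 15 µg, a dose contrast.
- B/Yamagata: 0 µg against 15 µg, a contrast of presence.

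**4. The plan's own sample size.** Section C.17.a does not state alpha; two-sided 0.05 is assumed. With unpooled variance,

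n = (1.960 + 0.842)² × [p₁(1−p₁) + p₂(1−p₂)] / (p₁−p₂)².

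For 50% against 25%: 7.85 × (0.25 + 0.1875) / 0.0625 ≈ 55 per arm. With 20% dropout, 2 × 55 / 0.80 = 137.5, rounded up to 138. This matches the plan. Every row of that table is labelled strain A, so neither correction changes it.

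**5. Illustration for B/Yamagata.** The documents give no B/Yamagata HAI rates. As assumptions, take seroprotection of 5-15% in HD-TIV (antigen absent) and 25-30% in SD-QIV (the plan's control range for protective titers), with 55 evaluable per arm and two-sided 0.05. With d = p_SD − p_HD,

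P(significant for SD-QIV) = Φ[(d − 1.96·SE₀) / SE₁], and P(significant for HD-TIV) = Φ[(−d − 1.96·SE₀) / SE₁],

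where SE₀ uses the mean of the two rates and SE₁ uses the separate rates.

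| HD-TIV | SD-QIV | Favours SD-QIV | Favours HD-TIV |
|---|---|---|---|
| 5% | 25% | 0.846 | <0.001 |
| 5% | 30% | 0.943 | <0.001 |
| 10% | 25% | 0.545 | <0.001 |
| 10% | 30% | 0.753 | <0.001 |
| 15% | 25% | 0.257 | 0.0005 |
| 15% | 30% | 0.469 | <0.001 |

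Worked row, 15% against 25%: SE₀ = √(2 × 0.2 × 0.8 / 55) = 0.0763 and SE₁ = √[(0.1275 + 0.1875) / 55] = 0.0757. Then (0.10 − 0.1495) / 0.0757 = −0.65, and Φ(−0.65) ≈ 0.26.

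Section C.17.b plans Bayesian estimates, not significance tests. The table therefore shows the direction and rough strength of the distortion, not the operating characteristics of the planned analysis.

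**The case against.** The other side has good points.

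- **The plural proves little.** Even the shared lineage supplies two B antigens over the enrolment years, B/Brisbane and then B/Colorado. Objective (i) does not name B/Yamagata. This stands: the fault is an unspecified lineage, not an explicit inclusion. The gap remains because section C.15.b generates the titers and no text sets them aside.
- **Measuring B/Yamagata is legitimate.** It is, and objective (vi), which covers all four antigens, is not directional. Only its use in a directional HD-TIV comparison is at fault.
- **The season list looks like text not carried forward.** Probably so, since sections C.1, C.4 and C.10 and Table 3 were updated for 2019-2020. But the sentence is the stated assay rule and does not present its seasons as examples.

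A reader might also infer more than the documents support:

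- **That objective (viii) cannot be answered for 2019-2020.** Two of the four strains are covered, section C.15.c sets no season limit on MN, and repeaters from 2017-2018 into 2018-2019 are unaffected.
- **That an HD-TIV advantage on B/Yamagata is impossible.** Section B.5 speaks of little to no protection, which is not zero and is not an HAI titer. Unlikely is the right word.
- **That SD-QIV gets four chances of success and HD-TIV three**, because the sample-size sentence refers to any one antigen. The table is strain A throughout, the primary objective is influenza A, and section C.17.b defines no any-antigen endpoint. Both vaccines contain two A strains.
- **That the PCR comparison is biased.** Section C.17.d compares "The percentage of individuals in each group that test positive for influenza by PCR" without splitting by type. Comparing two products as supplied is a legitimate question, and a missing lineage is part of a product's performance. Section B.5's figure of about 70% matched leaves about 30% of B infections, not of all influenza, and section B.1 says that most disease is influenza A. The documents do not allow the effect to be sized.

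**Conclusion.** Both points hold as errors of specification in secondary objectives.

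1. If section C.15.b is followed literally, 2019-2020 repeaters have no vaccine-matched HAI data for 2 of 2 influenza A strains under objective (viii). This rests on the strain lists alone. How many subjects are affected depends on how many repeat that season, which the documents do not give.
2. One of the two B lineages assayed is absent from HD-TIV in every season. Its between-arm contrast cannot be read as a dose effect and is unlikely to favour HD-TIV. The reasoning needs only the strain lists; the probabilities of below 0.1% and about 26% to 94% depend on the assumed rates.

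The primary influenza A objective in newly enrolled subjects, the randomization and the target of 138 are untouched.

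**What to change.** - **Section C.15.b:** state that HAI titers are determined for each antigen in the quadrivalent vaccine of the season in which the subject was vaccinated, including 2019-2020, for both the pre- and post-vaccination sera of that season.
- **Secondary objective (i):** restrict the directional comparison to the B/Victoria strain shared by both vaccines in each season. Report B/Yamagata separately and descriptively as an antigen contained only in SD-QIV.
- **Secondary objective (vi):** keep all four antigens, with the same note that B/Yamagata is not a dose comparison.
- **Section C.17.b:** list the antigens that enter each comparison, so that the choice is fixed before the titers are analysed.

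The cost is an edit to the protocol text and the use of the A/Brisbane/02/2018 and A/Kansas/14/2017 antigens in HAI assays already planned. Sample size, visits and blood volumes do not change.

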#### 4. Study Population:

1. **A target of at least 138 new subjects who received an allogeneic HSCT over two enrollment years: 2017-18 and 2018-2019. The following were the inclusion/exclusion criteria that were used:**

##### a. Inclusion criteria

1. Allogeneic HSCT recipients who are 3-23 months post-transplant;
2.  $\geq 18$  years of age;
3. Available for duration of study;
4. Patients with stable GVHD for at least 4 weeks will be eligible (stable is defined as no major change in systemic immunosuppressive therapy for worsening GVHD; adjustment of actual dose to obtain a stable target level is acceptable).
5. Can be reached by telephone and/or electronic communication
6. Subjects must have a platelet count of  $\geq 30,000$  to receive the immunizations. Patients requiring platelet transfusions are eligible to enroll and must have a platelet count  $\geq 30,000$  within 72 hours prior to their immunization, or platelet count  $\geq 75,000$  without transfusion documented within 30 days for subjects  $< 12$  months post-transplant and within 90 days for subjects 12-23 months post-transplant.

##### b. Exclusion criteria

1. History of hypersensitivity to previous influenza vaccination or severe hypersensitivity to eggs/egg protein;
2. History of Guillain-Barre syndrome;
3. Evidence of hematologic malignancy or disease relapse post-transplant (stable mixed chimerism is permitted);
4. History of receiving current seasonal influenza vaccine post-transplant;
5. Pregnant female;
6. History of proven influenza disease after September 1, 2018 prior to enrollment;
7. Non-allogeneic (e.g. autologous) or syngeneic hematopoietic SCT recipients;
8. History of known active infection with HIV
9. History of cirrhosis
10. History of known latex hypersensitivity;
11. Subjects who have received stem cell boost or delayed donor lymphocyte infusion within 90 days of enrollment, including day of enrollment
12. Receipt of. IVIG/SCIG  $< 28$  days prior to vaccination

**Criteria for temporarily delaying vaccine administration:** The following conditions are temporary or self-limiting, and a subject may be included in the study once the condition has resolved, provided that the subject is otherwise eligible:

1. Fever  $\geq 100.4^{\circ}\text{F}/38.0^{\circ}\text{C}$  (oral measurement), or an acute illness within 48 hours of enrollment
2. Receipt of any live vaccines within four weeks or any inactivated vaccines within two weeks prior to potential study vaccination.

Note: if patients were eligible for vaccine 1, they will be eligible to receive vaccine 2 regardless of any changes on their GVHD status, unless it is deemed not medically safe to receive influenza vaccine.

**For subjects who were enrolled and vaccinated in 2017-18, and 2018-19, the goal is to enroll these same subjects who participated the previous influenza season year and then administer the same vaccination as the previous year. These subjects are referred to as repeaters.**

**For example, subjects enrolled in 2017-18 year were eligible to enroll again in 2018-19 as repeaters. For subjects enrolled in 2018-19 year and received at least one vaccine, will be eligible to be enrolled as repeaters for 2019-2020 season.**

